## APPLICATION TO USE HUMAN RESEARCH SUBJECTS

---

9. This project will be conducted at the following location(s): (please indicate city & state)
- Purdue West Lafayette Campus
- Purdue Regional Campus (Specify): \_\_\_\_\_
- Other (Specify): Indiana Nutrition Education Program class locations throughout Indiana, these may include: Emergency food distribution centers; Supplemental Nutrition Assistance Program (SNAP) offices; Women, Infant, and Children Program (WIC) offices; participant homes
10. If this project will involve potentially vulnerable subject populations, please check all that apply.
- Minors under age 18
- Pregnant Women
- Fetus/fetal tissue
- [Prisoners Or Incarcerated Individuals](#)
- University Students (PSYC Dept. subject pool \_\_\_\_)
- Elderly Persons
- Economically/Educationally Disadvantaged Persons
- Mentally/Emotionally/Developmentally Disabled Persons
- Minority Groups and/or Non-English Speakers
- Intervention(s) that include medical or psychological treatment
11. Indicate the anticipated maximum number of subjects to be enrolled in this protocol as justified by the hypothesis and study procedures: 800 (400 for control group and 400 for experimental group)
12. This project involves the use of an **Investigational New Drug (IND)** or an **Approved Drug For An Unapproved Use**.
- YES       NO
- Drug name, IND number and company: \_\_\_\_\_
13. This project involves the use of an **Investigational Medical Device** or an **Approved Medical Device For An Unapproved Use**.
- YES       NO
- Device name, IDE number and company: \_\_\_\_\_
14. The project involves the use of [Radiation or Radioisotopes](#):
- YES       NO
15. Does this project call for: (check-mark all that apply to this study)
- Use of Voice, Video, Digital, or Image Recordings?
- Subject Compensation? Please indicate the maximum payment amount to subjects. \$100  
[Purdue's Human Subjects Payment Policy](#)      [Participant Payment Disclosure Form](#)
- VO2 Max Exercise?
- More Than Minimal Risk?
- Waiver of Informed Consent?
- Extra Costs To Subjects?
- The Use of Blood?      Total Amount of Blood \_\_\_\_\_  
Over Time Period (days) \_\_\_\_\_
- The Use of [rDNA or Biohazardous materials](#)?
- The Use of Human Tissue or Cell Lines?
- The Use of Other Fluids that Could Mask the Presence of Blood (Including Urine and Feces)?
- The Use of Protected Health Information (Obtained from Healthcare Practitioners or Institutions)?
- The Use of academic records?

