### **C. SUBJECTS TO BE INCLUDED**

**Describe:** The inclusion criteria for the study population includes: an interest in taking NEP lessons, willingness to wait 1 year to start NEP lessons, eligibility for SNAP, age of at least 18 years, not pregnant, living in a household located in Indiana, ability speak and read English, willingness to complete three 30 minute surveys at the designated time intervals, willingness to provide height and weight measurements, willingness to complete one 30 minute dietary recall and 60 minute FFQ at each assessment time point, willingness to stay in touch with NEP educators, and no previous participation in NEP lessons within the last year.

The exclusion criteria only include not meeting the inclusion criteria.

Women who are pregnant will not be able to enroll in the study; however, once recruited, participants who become pregnant during the study period will be able to continue participating in the study.

The study population may be considered vulnerable because they are a low income and low resource population that may have a lower than average level of education. Precautions will be taken to minimize potential risks to the study population.

The maximum number of participants targeted for the study is  $n=800$ ,  $n=400$  in the control group and  $n=400$  in the experimental group. Previous studies were used to calculate these estimates. Based on these “short term” studies, a 7% rate of attrition ( $n=17$  out of 236) is expected to increase to approximately 40% ( $n\approx 320$  of 800) in the proposed study due to the duration of 1 year between the post-assessment and the follow-up assessment. Based on these attrition considerations and our previous work, a sample size of  $n=800$  will be the recruitment goal (control group  $n=400$  and intervention group  $n=400$ ) with an approximate final sample size of  $n=480$  expected.

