**Nutrient Intake:** Mean usual nutrient intakes and distributions will be quantified at baseline and 1-year follow-up using the National Cancer Institute Method for estimating a single dietary component and change in intake from baseline and 1-year follow-up will be assessed and compared between the intervention and control groups. The website for instructions and SAS code are <https://epi.grants.cancer.gov/diet/usualintakes/>. Bootstrap methods will be applied to the data in order to estimate variability and compare mean usual intake estimates over time. Change in usual mean nutrient intake in the intervention group compared to the control group from baseline to 1 year follow-up is another primary outcome. The EAR for each nutrient will serve as the cutoff value to determine the percent of the population within the intervention and control groups that are at risk for nutrient inadequacy. Where an EAR does not exist, the percent of the population meeting or exceeding the AI will be used to determine the proportion of the population at low risk for nutrient inadequacy. The proportion of the populations at risk or at low risk is a third primary outcome and will be compared between the intervention and control groups and compared over the long-term to assess the impact of the intervention.

**Food Security:** The impact of the intervention on change in food security in the intervention group compared to the control group from baseline to 1-year follow-up will be assessed using a mixed regression model. Food security score may be used as a covariate in regression modeling or as a secondary outcome. Food security status will be characterized using the methods described in the US Guide to Measuring Food Security and in the USHFSSM survey.

**Body Mass Index (BMI):** BMI may be used as a covariate in regression modeling or as a secondary outcome.

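### The SAP counts inadequacy by an EAR cut-off for every nutrient with an EAR; if iron is analysed, this primary outcome would probably be misstated in menstruating-age women, in a direction set by their intake

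*SAP*

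**What the plan says.** The Nutrient Intake paragraph of the SAP has two branches. For nutrients with an EAR, "The EAR for each nutrient will serve as the cutoff value to determine the percent of the population within the intervention and control groups" at risk of inadequacy. For the others, "Where an EAR does not exist, the percent of the population meeting or exceeding the AI will be used" to describe the share at low risk. The SAP then states that "The proportion of the populations at risk or at low risk is a third primary outcome", to be compared between the groups and over the long term.

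Usual intake comes from the "National Cancer Institute Method for estimating a single dietary component", with bootstrap methods described for mean usual intakes. That model estimates the distribution of intake. The SAP names no requirement distribution, no probability method, no list of nutrients and no breakdown by sex or life stage for this outcome.

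Section C of the protocol admits people with "eligibility for SNAP, age of at least 18 years, not pregnant" at entry and sets no upper age limit. Women of menstruating age are therefore eligible, but neither document gives their expected share.

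**The concern.** The quantity of interest is the share of people whose usual intake is below their own requirement. The cut-off method replaces each person's requirement with one number, the EAR, which is the median requirement. The two kinds of misclassified people (above the EAR but short of their own need, and below it but adequately supplied) roughly cancel only under three conditions: requirements are about symmetric around the EAR, they vary less than intakes, and they are independent of intake.

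The SAP neither states these conditions nor exempts a nutrient that fails them. Iron in menstruating women is the obvious candidate, because menstrual losses can be expected to give requirements a long upper tail. If iron is analysed under the rule as written, both the level of a primary outcome and the between-arm change in it could be wrong. Using the same rule in both arms does not guarantee that the error cancels.

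**Working it through.** **Inputs from the documents.** The cut-off rule, its status as a primary outcome, and the eligibility of non-pregnant women from age 18. The plan gives no prevalence, effect size or power for this outcome, so there is no stated figure to reproduce.

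**Assumed inputs, varied.** In menstruating-age women, the iron requirement is lognormal with median (EAR) 8.1 mg/day and 97.5th percentile P = 14 or 18 mg/day. Usual intake is lognormal with mean M = 11, 13 or 15 mg/day and CV 25% or 35%, independent of requirement.

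**Formulas** (Φ is the standard normal distribution function):

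- Intake: sI = √ln(1 + CV²), μI = ln M − sI²/2
- Requirement: sR = ln(P/8.1)/1.96, which is 0.279 for P = 14 and 0.407 for P = 18
- Cut-off share: Φ[(ln 8.1 − μI)/sI]
- True share: Φ[(ln 8.1 − μI)/√(sI² + sR²)]

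**Worked case, M = 13, CV 25%.** sI = 0.246, μI = 2.535 and ln 8.1 = 2.092, so the numerator is −0.443.

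- Cut-off: Φ(−1.80) = 3.6%
- True, P = 14: Φ(−1.19) = 11.7%
- True, P = 18: Φ(−0.93) = 17.6%

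**Full grid.** The last two columns give the fall when intake rises by 10%. True values are for P = 14, then P = 18.

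| Mean, CV | Median intake / EAR | Cut-off % | True % | Cut-off fall, points | True fall, points |
|---|---|---|---|---|---|
| 11, 25% | 1.32 | 13.1 | 22.9, 28.1 | 6.5 | 7.0, 6.3 |
| 11, 35% | 1.28 | 23.3 | 28.6, 32.0 | 7.7 | 6.9, 6.1 |
| 13, 25% | 1.56 | 3.6 | 11.7, 17.6 | 2.2 | 4.3, 4.7 |
| 13, 35% | 1.51 | 11.1 | 17.3, 21.7 | 4.4 | 5.0, 4.9 |
| 15, 25% | 1.80 | 0.9 | 5.8, 10.9 | 0.6 | 2.4, 3.3 |
| 15, 35% | 1.75 | 5.0 | 10.2, 14.6 | 2.3 | 3.4, 3.7 |

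**Direction.** Every row above has median intake above the EAR, so every level is understated. With M = 7 and CV 25% (median 0.84 × EAR) the cut-off gives 76.3% against a true 68.2% (P = 14) or 64.4% (P = 18), an overstatement. In this model the error is zero when median intake equals the EAR.

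**Symmetry and spread.** At M = 13 with a normal requirement of CV 10%, the cut-off is within about 1 point: 3.6% v 4.6% at intake CV 25%, and 11.1% v 11.8% at CV 35%. With a normal requirement of CV 40% and intake CV 25%, it gives 3.6% v 13.8%. Symmetry alone is therefore not sufficient; the spread of requirements matters as well.

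**Whole arm.** If these women are a share f of an arm and the rule is accurate for everyone else, the arm-level error is f × (true − cut-off). Over the grid, f = 20% to 60% gives 0.2 × (5.8 − 0.9) = 1.0 point up to 0.6 × (28.1 − 13.1) = 9.0 points.

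**The case against.** The strongest reply is that neither document mentions iron, lists the nutrients, or gives any iron requirement or intake. The skew of iron requirements is general physiology that the documents cannot confirm. That stands, and it makes the iron result conditional. It does not remove the point: the rule covers every nutrient with an EAR and the plan never states or checks what the rule assumes.

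A reader might infer that iron inadequacy is bound to be understated. The documents do not support this. The sign depends on where median intake lies relative to the EAR, which they do not give, and it reverses below the EAR.

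A reader might also infer that the trial would miss a real improvement. That too depends on the inputs. In the grid, the cut-off shows a smaller change than the true one in some rows, about the same in others, and a larger one at mean 11, CV 35%.

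It would also be too wide to say that the cut-off is applied to all nutrients, since those without an EAR go to the AI branch, or that it is unsound in general. With a narrow, symmetric requirement it performs well. Finally, the outcome is defined for whole arms, so the subgroup figures overstate the effect on the reported proportion.

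**Conclusion.** The point holds conditionally. Followed as written, the SAP applies the cut-off to any nutrient with an EAR, including one whose requirements break the method's assumptions, and it does so in a primary outcome. If iron is analysed and requirements in menstruating-age women are wide and right-skewed, their inadequacy is misstated: too low if median intake exceeds the EAR, too high if it is below.

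For assumed intakes above the EAR, the subgroup figures are 1-23% by cut-off against 6-32% true. The change for a 10% rise in intake ranges from understated (2.2 v 4.3-4.7 points at mean 13, CV 25%), through nearly unaffected (6.5 v 6.3-7.0 at mean 11, CV 25%), to overstated (7.7 v 6.1-6.9 at mean 11, CV 35%). All of this rests on the lognormal shapes, on independence of intake and requirement, and on requirement and intake values that the documents do not supply. No trial-specific error can be stated. The change is worth making before analysis, but it concerns one probable nutrient in one subgroup of one of several primary outcomes.

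**What to change.** In the Nutrient Intake paragraph of the SAP:

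- List the nutrients in the third primary outcome.
- Limit the EAR cut-off to those whose requirements are approximately symmetric and vary less than intakes.
- If iron is included, use the probability method for menstruating-age women: take the probability of inadequacy at each usual intake from a published requirement distribution and average it over that subgroup's usual-intake distribution from the same NCI model. Combine the result with the cut-off result for the rest of the arm, weighted by share. Run the whole calculation inside a bootstrap, since the SAP describes its bootstrap for mean intakes.
- Alternatively, leave iron out of this outcome and say so.

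The cost is SAP wording and a few lines of code on output already planned. No new dietary data are needed. The downsides are that a requirement distribution by age and sex must be chosen and cited in advance, that iron is then computed by a different formula from the other nutrients, and that the probability method still assumes intake and requirement are independent.

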
In addition to the survey, dietary recalls, and FFQ, NEP educators will take height and weight measurements on each participant at each assessment time point. Weights will be measured using the SECA 869 mobile medical flat scale with remote display. Heights will be measured using the SECA 213 mobile stadiometer. This weight scale and stadiometer are research grade measurement tools. Height and weight measurements will be taken following the Centers for Disease Control and Prevention (CDC) National Health and Nutrition Examination Survey (NHANES) anthropometry manual guidelines. Height and weight measurements will be completed in a private setting or privacy screens will be used. Only the NEP educators will be able to see the measurements. Three measurements will be taken at each assessment time point in order to calculate an average. Participants will be allowed to know their measurements upon request at the time of measurement. Researchers will use these measurements to calculate BMI.

An in person survey, two dietary recalls, one FFQ, and height and weight measurements will be completed for each participant at each of the three assessment time points. The first and third assessments will cover a reference period the past 12 months, while the second assessment will cover the past 30 days. Participants randomized to the control group will be provided the opportunity to complete the SNAP-Education program at the completion of the study.

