## SNAP-Ed Sequel Statistical Analysis Plan

**Methods:** Up to 2 repeated online 24 hour dietary recalls using the Automated Self-Assisted 24-hour Recall (ASA-24) and the Diet History Questionnaire II (DHQ II) (web-based food frequency questionnaire) developed and provided by the National Cancer Institute will be used to estimate dietary intake; the Estimated Average Requirements (EAR) for nutrients (or Adequate Intake(AI) for nutrients that do not have an EAR) will be used as a dietary reference; the Healthy Eating Index-2010 will be used to characterize diet quality using data collected from the ASA-24; the 18-item US Household Food Security Survey Module (USHFSSM) will be used to assess household food security; the Nutrition Education Program (NEP) Medium Term Survey and additional questions will be used to assess participant characteristics, nutrition and health knowledge, and nutrition and health behavior

**Characteristics:** Study participant characteristics at baseline will be compared across the intervention and control groups to test for potential confounders to test for in regression models. Characteristics of participants who withdrew from the study will also be compared to those who completed the study.

**Diet Quality:** The Healthy Eating Index-2010 scoring algorithm will be used to characterize diet quality. Instructions and sample SAS code are provided by the National Cancer Institute website at <https://epi.grants.cancer.gov/hei/>. The simple algorithm will be used in order to assign HEI scores to each individual to be able to match and compare individual participants over time using regression modeling. Change in diet quality in the intervention group compared to the control group over time is one primary outcome.

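### Three primary outcomes, at least one of them run nutrient by nutrient with no nutrient list, and no rule for overall error: at 0.05 per test with any one result counting as success, the false-positive chance exceeds 5%

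*SAP*

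**What the plan says.** The SAP labels three outcomes primary.

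- **Diet quality:** "Change in diet quality in the intervention group compared to the control group over time is one primary outcome".
- **Nutrient means:** "Change in usual mean nutrient intake in the intervention group compared to the control group from baseline to 1 year follow-up is another primary outcome". These are estimated "using the National Cancer Institute Method for estimating a single dietary component", so the model handles one nutrient at a time. That this outcome produces a separate test per nutrient is an inference from the method; the SAP does not say so outright.
- **Proportions:** "The proportion of the populations at risk or at low risk is a third primary outcome". Here the SAP is explicit: "The EAR for each nutrient will serve as the cutoff value to determine the percent of the population", with the AI used where no EAR exists. The proportions are to be "compared between the intervention and control groups and compared over the long-term to assess the impact of the intervention".

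The SAP's Methods paragraph refers to "Estimated Average Requirements (EAR) for nutrients (or Adequate Intake(AI) for nutrients that do not have an EAR", so more than one nutrient is meant, but neither document names or counts them. Neither document states a significance level, an order of testing, a requirement that all primaries succeed, or an adjustment for multiple tests.

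On timing, Protocol section B says "two dietary recalls, one FFQ, and height and weight measurements will be completed for each participant at each of the three assessment time points". Protocol section A sets a goal covering both immediate and long-term diet quality, and equates long-term with one year.

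**The concern.** Several primary outcomes are acceptable if the plan says how they combine into a conclusion. This plan does not, and the number of primary tests cannot be counted from it because the nutrient list is missing. Someone analysing the data could test many nutrients, find one or two significant, and report a primary effect without departing from anything written. A reader could not tell how many tests had been available.

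The HEI outcome adds a smaller freedom. Over time could mean the change to the second assessment, the change to the 1-year assessment, or a single group-by-time test across all three.

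Protocol section A says the results may support changes to the programme or to policy, so a chance finding reported as primary would matter.

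**Working it through.** **Figures in the plan.** There is no stated error rate to reproduce. The only sample-size arithmetic is in Protocol section C: 800 recruited with about 40% attrition gives 800 × 0.60 = 480, which agrees with the stated 480. It is used below only for the cost of the fix.

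**Inputs.**
- From the documents: three primary outcomes; 480 expected completers.
- Assumed: two-sided 0.05 per test; any one significant test counts as success; *k* nutrients, each with one test of the mean and one of the proportion, plus one HEI test, giving 2*k* + 1 tests; all correlations; completers split equally, 240 per arm.

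**Step 1: one test per named outcome (3 tests).**
- Independent: 1 − 0.95³ = 0.143.
- Equal correlation 0.5 (simulated, 200,000 null trials): 0.125.
- Equal correlation 0.9 (same simulation): 0.084.

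So about 8-14%. Only perfect correlation brings it down to 5%.

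**Step 2: *k* nutrients, high end.** Assume independent nutrients, HEI independent of them, and correlation 0.8 between a nutrient's mean and its own proportion. The bivariate normal probability that neither of a nutrient's two tests is significant is *q* = 0.9219. The chance of at least one significant test is 1 − 0.95 × *q*^*k*:
- *k* = 3 (7 tests): 0.256
- *k* = 10 (21 tests): 0.579
- *k* = 20 (41 tests): 0.813

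**Step 3: *k* nutrients, low end.** Assume correlation 0.9 between nutrients, 0.95 between a nutrient's mean and its proportion, and 0.5 between HEI and the nutrient means. Simulation (1,000,000 null trials) gives 0.146, 0.209 and 0.251 for *k* = 3, 10 and 20. With the between-nutrient correlation at 0.7 instead, the values are 0.171, 0.294 and 0.387.

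The ranges are therefore about 15-26%, 21-58% and 25-81%. They illustrate the effect and are not bounds.

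**Step 4: cost of Holm.** The smallest p-value must fall below 0.05/(2*k* + 1): 0.05/7 = 0.0071, 0.05/21 = 0.0024, 0.05/41 = 0.0012. For a comparison of two means with 240 per arm, the difference detectable with 80% power, in SD units, is (z + 0.842) × √(2/240), where √(2/240) = 0.0913:
- threshold 0.05: (1.960 + 0.842) × 0.0913 = 0.256
- threshold 0.0071: (2.690 + 0.842) × 0.0913 = 0.322
- threshold 0.0024: (3.038 + 0.842) × 0.0913 = 0.354
- threshold 0.0012: (3.234 + 0.842) × 0.0913 = 0.372

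These ignore clustering by educator and the estimation error in usual intake. They do not apply to the proportions.

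**The case against.** **The harm is conditional.** It needs both 0.05 per test and a rule that any one significant result is enough, and the SAP states neither. At 0.01 per test, three independent tests give 1 − 0.99³ = 0.030, below 5%. Parts of the Nutrient Intake section also read as estimation: distributions, percentages at risk, bootstrap variability. This stands as a limit on the claim. It does not remove it, because the SAP calls these outcomes primary and leaves the choice of rule open until after the results are seen.

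**The size is mostly assumed.** Nutrient count, alpha and correlations all come from outside the documents. This also stands: other correlation patterns give other figures. What is robust is the direction, since the excess persists at every correlation short of perfect.

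**Tempting stronger readings.**
- A reader might infer that the time point of the proportions is as open as that of HEI. It is not. The SAP quantifies the intake distributions at baseline and 1-year follow-up, and Protocol section A defines long-term as one year. What remains unclear is whether comparing between groups and over the long term means one test of the difference in change or two tests.
- A reader might count HEI at both follow-ups and each proportion both between arms and over time, and so reach far larger error rates. The text does not support that count: HEI over time is equally consistent with one group-by-time test. Moreover, a within-arm change is not null merely because SNAP-Ed has no effect, since season, secular trend or regression to the mean can produce it. Treating it as a false positive for the intervention would be wrong.
- A reader might conclude that HEI must be the only primary. Nothing in the documents requires this. Protocol section A also names BMI and food security among its goals.

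**Conclusion.** The point holds, in conditional form. Three outcomes are called primary, one is explicitly and another by inference tested per nutrient, the nutrients are unlisted, and nothing governs overall error or defines success. The HEI time point is open, and the form of the proportion comparison is ambiguous although its 1-year time frame is clear.

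With two-sided 0.05 per test and any single result taken as success, the false-positive chance is above 5%. Roughly 8-14% applies at the smallest count of three tests. It rises with the number of nutrients, and its size cannot be fixed from the documents. The plan does not commit to this rule, so it cannot be said that the trial will have an inflated error rate, only that the plan does not prevent one. This should be corrected before analysis.

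**What to change.** Before analysis, amend the SAP to:

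1. List the nutrients, marking which use an EAR and which an AI.
2. Name one between-arm contrast and one time point for each primary outcome. For the proportions, use the between-arm difference in change from baseline to 1 year. For HEI-2010, choose one follow-up or one group-by-time test.
3. State the significance level, and control family-wise error across all primary tests. Holm is one suitable choice, because it is valid under any dependence between tests and keeps all three outcomes primary.

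Making HEI-2010 the sole primary, with the nutrient outcomes as a listed secondary family, is an option if the sponsor prefers it, but is not needed to cure the defect.

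No new data are required. The price is stricter thresholds for every primary test, HEI included, with the loss of sensitivity shown in the last step of the working. A shorter nutrient list reduces that loss. The effect on power for the proportions needs its own calculation, for which the documents give no inputs.
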